Surgical service lines will include orthopedic total joint, orthopedic spine, gynecology/oncology, thoracic, general, hernia, colorectal, open vascular, plastic, and open urological procedures. These lines will be randomized 1:1 to either the bundle of activities or usual care. The unit of randomization is the service line. The perioperative environment (the patient, the patient to follow, and all providers caring for the patient and the patient to follow) for the randomized service line (treatment or usual care) will be involved in surveillance. This means that all patients, all providers caring for those patients (changes day by day), and care environments (equipment and stopcock sets) will be involved in surveillance. Surveillance from treatment and control groups will yield *S. aureus* transmission events that will be processed to guide proactive improvements in the treatment bundle.

Treatment group (bundle) inclusion/exclusion criteria:

Inclusion criteria: Patients seen at UIHC who are scheduled to undergo surgery from providers in one of the service lines above, documentation of informed, written consent, >18 years of age, procedure requiring general/regional anesthesia.

Exclusion criteria: Lack of documented informed, written consent, patients <18 years of age, procedures outside of the surgical service lines listed above, not requiring general/regional anesthesia, patients not seen in the UIHC clinics, and an allergy to iodine/shellfish or chlorhexidine.

Usual care group (existing practice at UIHC) inclusion/exclusion criteria:

Inclusion criteria: Patients seen at UIHC who are scheduled to undergo surgery from providers in one of the service lines above, documentation of informed, written consent, >18 years of age, procedure requiring general/regional anesthesia.

Exclusion criteria: Lack of documented informed, written consent, patients <18 years of age, procedures outside of the surgical service lines listed above, not requiring general/regional anesthesia, patients not seen at UIHC, and an allergy to iodine/shellfish or chlorhexidine.

VI.14

Provide an estimate of the total number of subjects that would be eligible for inclusion in each of your study populations (include your control population if applicable)

We anticipate that >80% of all patients undergoing surgery in the surgical service lines above will be eligible for the study.

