We do not know what the service line will be for the treatment and control until we randomize. We do not know exactly how many patients each line will see over the next 2 years. There are 24,000 patients that undergo adult surgery at UIHC each year. Over two years, that is 48,000 patients. The lines selected in total represent >80%, at least 38,400. That is 3840 per line, or roughly 1500 patients each year per line. Thus, we expect that 80%, or roughly 1200 patients, will be eligible for the study for each line over the 2 year period. In terms of providers, approximately 10 providers will be involved in the care of each patient in the OR and discharge area combined. Thus, over two years, there will be 12,000 providers (not exclusive; as providers may be repeatedly sampled over the two year period).

Treatment group (bundle): 80% of all patients in the randomized service lines are expected to be eligible, N=1200 for each service line. We expect participation from the majority (>80%) of providers in the OR and in the discharge area, N=12,000 providers for each line.

Usual care group: 80% of all patients in the randomized service lines are expected to be eligible, N=1200 for each service line. We expect participation from the majority (>80%) of providers in the OR and in the discharge area, N=12,000 providers for each line.

VI.15

Describe how you will have access to each of your study populations in sufficient number to meet your recruitment goals.

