We will be attempting to capture all patients that meet inclusion criteria which could include patients seen and consented in the clinic, seen and consented on the hospital floor, intensive care units (inpatient surgery), or pre-anesthesia testing (PAT). Any patient meeting inclusion criteria that the surgeon obtains surgical consent for could be captured. Poster reminders will be placed in the clinics, on the ward, and PAT. The study consent forms will be attached to the surgical consent forms. Surgical providers obtaining surgical consent will obtain study consent when possible. This will otherwise be executed via our research team via pager. Preoperative kit orders will be completed by surgical providers or physician study team members when needed. The signed and held order will populate a list in EPIC for the PI ([name]) that will be filtered by type of surgery, surgeon, and date of surgery within 10 days. It will include the patient medical record number, address/phone number, and an icon indicating the POC signed and held order. [name] will work the list to send ordered kits to patients. [name] will enter a new signed and held order for the kit and will associate the assigned kit number with the order, which will create a new ICON indicating ordered kit sent to patient. This will also update the Clarity report in EPIC with the kit number in addition to the other previously mentioned fields. The patient will receive the kit along with a reminder for why they received the kit (see attached in miscellaneous), use the kit (up to 3 reminders will be provided by [name] study team), and RDB will receive and process the kits. Patients will use a prepaid mailer to send the kits to RDB which will have the RDB address in the send and return fields so that patients are not revealing their identity to RDB (process okay per USPS). RDB will send returned kit numbers to [name] daily. [name] will complete the signed and held orders for patients in the Clarity report that returned kits for processing. The completed POC will generate another ICON indicating received and processed and will again update the Clarity report. The research assistants will work the list to select 2 patients with completed POC orders, treatment and control, for OR PathTrac Observation each day. The assistants will confirm 1st patient consent. Once confirmed, an OR PathTrac Kit will be ordered in EPIC which creates an ICON indicating consent confirmed, a consent confirmed box checked in the RDB microEMR will be placed (3 ways for tracking consents, the written document and two electronic confirmations), and the preoperative swab and OR PathTrac kit numbers entered into the microEMR along with baseline patient demographic information (OR room number and case number, surgery duration, date and time). Informed, written consent will be obtained from the second patient on the day of surgery (see attached consent for patient 2), an OR PathTrac Kit ordered, demographic information (see previous) entered into the microEMR, and surveillance completed. If the second patient does not provide consent for their samples, the pair will be excluded and recruitment continued to reach 1,000 pairs. Our prior experience and recent experience at the University of Iowa strongly suggests that patient refusal to provide written consent for intraoperative cultures will be a rare event. The assistant will then follow the 1st patient to the recovery area for sampling as previously described using the Ward Environment Surveillance (WES) kits. The WES kit number will be associated by the micro EMR to the other kit units. This

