- Other - The attached poster which summarizes elements of the study consent will be made available as a visual aide/reminder for both the surgical team and the patients.
 - Consent Document

- VII.D.16** ***Are you requesting a waiver of documentation of consent (either no subject signature or no written document)?***
Yes

- VII.D.17** ***Choose one of the following to indicate why you are requesting that the IRB waive the requirement to obtain a subject signature as documentation of consent:***
- A.** The research presents no more than minimal risk (minimal risk means the probability and magnitude of harm or discomfort anticipated in the research are not greater in and of themselves than those ordinarily encountered in daily life or during the performance of routine physical or psychological examinations or tests)

AND

The study involves no procedures for which consent is normally required outside of a research context. *(This type of waiver is often permitted for a minimal risk mail-out survey that includes a cover letter with all elements of consent, and returning the survey indicates consent. You cannot request this waiver if the study also involves the use of any protected health information (PHI).)*

- VII.D.18** ***Explain why this meets the chosen criteria in A. or B. above:***
This applies only to the clinician subjects, and, this is minimal risk. We are not collecting provider identifiers. All bacteria collected from providers will receive a unique barcode that will not be linked to the specific provider, only to the type of provider (anesthesia attending or anesthesia assistant).

- VII.D.19** ***Before the subject gives consent to participate are there any screening questions that you need to directly ask the potential subject to determine eligibility for the study?***
Yes

- VII.D.20** ***List any screening questions you will directly ask the potential subject to determine eligibility.***
Are you allergic to iodine, shellfish, or chlorhexidine? If the answer is yes, they will not be enrolled

- VII.D.21** ***Will you keep a screening log or other record that would include information on people who do not enroll in the study?***
Yes

- VII.D.22** ***Describe the information being collected and the purpose for keeping this information.***
For each service line, we will collect age and sex for those patients so that we can assess for biases, such as selection bias.

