Reducing Perioperative S. aureus Transmission via use of an Evidence-Based, Multimodal Program Driven by an Innovative Software Platform (OR PathTrac)

9/20/2018

Statistical Analysis

Multiple statistical methods were used. For simplification, we list the statistical methods in the precise sequence they are reported in the results.

The Fisher exact test was used to compare patient and procedural demographic information for treatment vs control groups and for cases involving *S* aureus transmission. Similarly, the distribution of patients by ASA scores greater than 2 and by sex for enrolled vs eligible patients were compared by surgeon using the Mantel-Haenszel test.

The Fisher exact test was also used to examine the potential association of each of the covariates mentioned earlier with *S aureus* transmission. None were associated.

A 2-sided Wilcoxon-Mann-Whitney test was used to examine the association of treatment assignment with the number of transmitted *S aureus* isolates. Poisson regression was used to estimate the incidence risk ratio (IRR) of *S aureus* transmission for the independent variable of treatment. Poisson regression was used to estimate the IRR because the incidence of transmission was so large (ie, much greater than 10%) that the odds ratio estimated using logistic regression would be a biased estimator of the relative risk.²⁴ We repeated the analysis using multilevel Poisson regression clustering by surgeon or specialty.

The Fisher exact test was used to compare the proportion of patients in the treatment group with transmission events before vs after surveillance feedback and the proportion of patients with SSI with and without documented *S aureus* transmission. Poisson regression was used to compare the proportion of patients with SSI with and without documented *S aureus* transmission, clustered by surgeon.

The proportion of patients with SSIs was compared with the Fisher exact test. Time to infection was evaluated by Cox proportional hazard modeling. We repeated the analysis using multilevel Poisson regression clustering by surgeon and specialty.

There were no missing data for the primary and secondary outcomes. Calculations were performed using Stata version 16.1 (StataCorp). All P values were 2-sided, and P < .05 was taken to indicate statistical significance.

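### The only enrolled-versus-eligible check is stratified by surgeon, so it cannot show uneven enrolment between surgeons, lines or arms; if the eligible include the enrolled, it is also conservative within surgeons

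*SAP*

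**What the plan says.** The SAP (Statistical Analysis, second paragraph) has one comparison of enrolled with eligible patients. It covers ASA scores above 2 and sex, which "by sex for enrolled vs eligible patients were compared by surgeon using the Mantel-Haenszel test". The natural reading is that surgeon is the stratifier. Neither document says whether eligible means all eligible patients, including those enrolled, or only those not enrolled. The test is two-sided at 5% ("All P values were 2-sided, and P < .05 was taken to indicate statistical significance").

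The protocol gives the setting:

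- VI.13: "The unit of randomization is the service line".
- VII.D.29: treatment or control kits are sent according to line, so a patient's arm is fixed by the line before that patient consents.
- VI.15: "Surgical providers obtaining surgical consent will obtain study consent when possible"; otherwise the research team is paged to do it.
- VII.D.21-22: a log will hold "information on people who do not enroll in the study", and its purpose is stated at the level of the line: "For each service line, we will collect age and sex for those patients so that we can assess for biases, such as selection bias".
- VI.14, on the eligible pool: "80% of all patients in the randomized service lines are expected to be eligible, N=1200 for each service line".

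**The concern.** In a trial that randomises lines and then recruits patients, the selection that matters most is selection that differs between arms. If consent is sought through surgeons as circumstances allow, uptake can differ from surgeon to surgeon. Where surgeons with sicker patients enrol a smaller share of them, the enrolled case mix of that line, and so of that arm, shifts. A test that looks only inside each surgeon's practice cannot register this. A null result could then be read as showing no selection when the question posed for each service line was not examined.

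A second, conditional issue concerns the two groups compared. If the enrolled are counted among the eligible, they appear on both sides of the test. That shrinks the difference and makes the test reject too seldom.

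**Working it through.** The documents state no result or count for this check, so there is no figure to reproduce. The two parts are taken separately.

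**1. Between surgeons.** Let surgeon k have N_k eligible patients, prevalence p_k of the trait and enrolment fraction f_k, choosing at random among his or her own patients. Within every surgeon the odds ratio is 1, so the Mantel-Haenszel odds ratio is 1 whatever the f_k. The overall prevalence among the enrolled is Σ f_k N_k p_k / Σ f_k N_k, which does depend on them. If each surgeon works in one line (an assumption), every stratum lies in one arm, so line and arm differences are removed as well.

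Assumed scenario: 40 surgeons with 300 eligible patients each; half have prevalence 35% and half 65%, so 50% overall; 20,000 simulated runs. Arithmetic for the first row: (0.05×0.35 + 0.117×0.65)/0.167 = 56.0%.

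| Enrolment (35% / 65% surgeons) | Trait among enrolled | Stratified, separate groups | Stratified, overlapping groups | Crude, separate groups |
|---|---|---|---|---|
| 5% / 11.7% | 56.0% | 5.0% | 3.1% | 98% |
| 15% / 31.7% | 55.4% | 5.1% | 1.2% | 100% |
| 30% / 70% | 56.0% | 5.0% | 0.03% | 100% |

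The last three columns are rejection rates. The crude test here treats patients as independent; an interval allowing for clustering would be wider.

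By arm, also assumed: in the bundle arm, half the surgeons have 60% ASA>2 and enrol 16.7%, and half have 30% and enrol 30%. Control surgeons have the same mix and enrol evenly.

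- Bundle, enrolled: (0.167×0.60 + 0.30×0.30)/0.467 = 40.7%.
- Bundle, not enrolled: (0.833×0.60 + 0.70×0.30)/1.533 = 46.3%, so the difference is −5.6 points.
- Control: 45.0% in both groups, difference 0. The between-arm contrast is −5.6 points.
- The surgeon-stratified odds ratio is 1.00 throughout.

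**2. Overlap, only if the eligible include the enrolled.** Let n be enrolled, N eligible, f = n/N, and q = 1−p.

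- Difference: p_enrolled − p_eligible = (1−f)(p_enrolled − p_not enrolled).
- Variance the test assumes: pq(1/n + 1/N) = pq(1+f)/n.
- True variance: pq(1/n − 1/N) = pq(1−f)/n.
- The z statistic is therefore that of the separate-groups test multiplied by s = √((1−f)/(1+f)).
- True size = 2(1 − Φ(1.96/s)). Where separate groups would give 80% power, power = Φ(2.80 − 1.96/s).

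Example at f = 0.233: s = √(0.767/1.233) = 0.788; 1.96/0.788 = 2.49; power = Φ(0.31) = 62% (simulated 63%).

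| Enrolled / eligible (assumed) | f | s | True size | Power |
|---|---|---|---|---|
| 1,000 / 30,720 | 0.033 | 0.968 | 4.3% | 78% |
| 1,000 / 12,000 | 0.083 | 0.920 | 3.3% | 75% |
| 1,400 / 12,000 | 0.117 | 0.889 | 2.8% | 73% |
| 2,800 / 12,000 | 0.233 | 0.788 | 1.3% | 62-63% |
| 2,800 / 7,200 | 0.389 | 0.663 | 0.3% | 44% |

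Sources for the counts:

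- Numerators: 1,000 is one index patient per case pair (XI.1). 2,800 is the consent target (XI.2); it includes second patients, whom the research team approaches on the day of surgery (VI.15). 1,400 assumes that target splits evenly.
- Denominators: 12,000 is 10 × 1,200 and 7,200 is 6 × 1,200, because XI.2 mentions both up to ten lines and six. 30,720 is 80% of 38,400 (VI.14).
- VI.14 is itself inconsistent: 80% of 3,840 per line is 3,072, not 1,200.

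For index patients the plausible fractions are about 3-12%. The last two rows are upper cases.

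**The case against.** **The stratified test is a proper test.** This stands. Case mix differs legitimately between surgeons, and stratifying is the right way to look for selection within a practice. The gap is that nothing accompanies it. A reader might infer that the test is wrong and should be dropped; the documents do not support that.

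**Arm imbalance is checked elsewhere.** The sentence before it in the SAP compares treatment and control demographics by Fisher's exact test, not stratified by surgeon, and protocol XI.2 plans a balance assessment. This softens the concern. In the arm example above, the table would display 40.7% against 45.0%. But that comparison describes enrolled patients, so it cannot separate enrolment selection from case-mix differences among the few randomised lines. Its power is also limited: with 500 per arm, z = 0.043/√((0.407×0.593 + 0.45×0.55)/500) = 1.38, about 28%. With 1,400 per arm it is about 63%.

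**The overlap may not exist.** This also stands. A reader might take under-detection within surgeons as established. The literal wording suggests nested groups, but eligible is undefined and the protocol planned a log of people who do not enrol. If the groups are separate, nothing is lost.

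**The mechanism is assumed.** The surgeon scenarios show what is possible, not what is likely. Protocol VI.15 has the research team obtain consent where surgeons do not, which weakens the surgeon-driven route. Nothing in the documents shows that selection occurred, that the arms differ, or that the primary result is biased, and none of these should be inferred.

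**Conclusion.** The point holds as a limit of scope. The surgeon-stratified check cannot reveal uneven enrolment between surgeons, and hence between lines or arms, so it does not answer the question that protocol VII.D.22 set for each service line. This follows from the algebra of the test and needs no assumption about counts; only the illustrated sizes do.

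The overlap point is conditional on eligible including the enrolled. The loss is then small at fractions plausible for index patients (80% power becomes about 73-78% at 3-12%) and material only at higher fractions (62-63% at 23%). Those fractions are assumptions.

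This concerns an ancillary check. It bears on how far a null result may reassure, not on the primary estimate.

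**What to change.** 1. Define eligible, and compare enrolled patients with eligible patients who were not enrolled. If the eligible counts include the enrolled, subtract them surgeon by surgeon.
2. Keep the surgeon-stratified Mantel-Haenszel result, described as a test of selection within surgeons.
3. Add, within each arm and by service line, the unstratified enrolled-minus-not-enrolled difference in ASA>2 and in sex, and the contrast of that difference between arms. Give intervals that allow for clustering by surgeon or line; with so few lines, descriptive reporting is acceptable.
4. State that the treatment-versus-control Fisher comparison describes enrolled patients and does not by itself identify enrolment selection.

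The cost is one definition and a few table rows. The existing check already needs ASA, sex and surgeon for eligible patients, and arm follows from line. (The protocol's log names only age and sex, so ASA for the non-enrolled must come from whatever source the SAP check used.) There is one small downside. Observation needs a following case in the same operating room and one pair per arm per weekday, so sampling fractions can differ between surgeons for scheduling reasons. The unstratified rows will reflect that too and must be read beside the stratified result.

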Kits will be transported to RDB Bioinformatics laboratory for processing following sample acquisition. The dynamic surveillance software platform will guide proven, systematic phenotypic and genomic processing of collected samples in order to identify clonal transmission events occurring within and between operating room reservoirs in the observational unit (case pair). Guidance will be based on the strength of epidemiological-relatedness as follows: A transmission event will be defined as the presence of one or more isolates in a measured reservoir that was not present at case start. Transmission events within an observational unit will be further analyzed as directed by the RDB platform to identify clonally-related *S. aureus* transmission events.

The RDB Bioinformatics software platform will process transmission dynamics in order to continually summarize the epidemiology of *S. aureus* transmission. This information will be continually displayed in order to identify the most common reservoir of origin, the most common transmission locations (vectors), the most common mode of transmission (vertical or horizontal), and involvement of key portals of entry (stopcocks). To address strain characteristics, reports will focus on more pathogenic strains defined by the top 5 most transmissible, resistant, and virulent strain characteristics.

Automated analysis reports for overall transmission and for transmission of more pathogenic strains will be used by the infection control perioperative team to continually optimize the interventions affecting all patients in the treatment clusters as described further below. The platform will automatically quantify transmission events occurring in

treatment and control clusters such that involved in data collection and data entry will be blinded to the primary outcome.

All data will be analyzed by the statistician ([name]) at Dartmouth Hitchcock Medical Center who will not be involved in data collection.

Work flow: Monday-Friday only. Limited to patients that are seen in UIHC clinics. 1,000 case pairs: (500 treatment and 500 usual care) will be studied during the 2-year study period. This corresponds to one case pair in the “bundle” group and one case pair in the usual care group each day (5 days a week for 50 weeks each year). All patients will be followed for 90 days for infection development.

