 - Improved environmental cleaning: Environments (OR and ward) affected by high-risk S. aureus transmission events will be mapped by surveillance and addressed by automated reporting to the anesthesia workroom supervisor. This will trigger improvements in routine (standard cleaning using quaternary ammonium compound and micro cloth followed by a surface disinfection wipe) and terminal [improved routine technique followed by employment of robotic cleaning (Ultraviolet light)] cleaning.
- Fatigue mitigation: The team will use surveillance to continually monitor the impact and fatigue of the proposed interventions as conveyed by failure mode analysis of transmission dynamics involved clonal S. aureus transmission.

XI.2

Provide the rationale or power analysis to support the number of subjects proposed to complete this study.

Statistical Analysis: The unadjusted primary intention to treat analysis will compare the proportion of clonally-related S. aureus transmission events occurring in treatment vs. control perioperative (preoperative, intraoperative case pair, and postoperative) observational units across the 6 randomized service lines using the Chi squared test. We will assess for balance for variables known to be associated with intraoperative

transmission (case, duration > 2 hours, and discharge location). In the case of imbalance, we will use multivariate techniques to further explore the treatment effect using a generalized linear models approach.

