Initial Power Analysis (see amendment below based on reviewer concerns): We intend to screen a total of 1000 patients for up to 10 surgical service lines. Service lines will be randomized 1:1, yielding 500 patients in each treatment arm. Each patient will provide 4 observational units that include preoperative to intraoperative, intraoperative case 1 to intraoperative case 2, intraoperative case 1 to postoperative, and preoperative to postoperative opportunities for detection of *S. aureus* transmission. Thus, 500 patients in each arm will provide 2,000 observational units for a total of 4,000 observational units during the two-year study period. We originally calculated that this provided 90% power to detect a 30% relative reduction in the primary outcome (10.58% down to 7.41%). The estimated clonally related *S. aureus* transmission rate was based on a previously reported detection rate of 58 events in 548 observational units for all-comers to the operating room at 3 major academic medical centers in the United States. To address service line variation, we supposed that the logit-frequencies of the primary outcome for each service line were distributed as a normal distribution with a mean of -0.41 and standard deviation of 0.20. This amount of between-line variation corresponds to an intra-cluster correlation (ICC) of approximately 1%. It can also be interpreted as the amount of variation in which service lines in the top quartile of rates would have an average frequency (after removing within subsection binomial variation) of 46% while service lines in the lowest quartile have an average frequency of 33%. These calculations were accomplished using Monte Carlo simulations written in R 3.3, and using in part the following approximation for the ICC when rates are logit-normal, $1/(1+1/\sigma^2 \cdot \pi^2 \cdot \text{pa}(1-\text{pa}))$ (which can be readily derived using the delta theorem) where pa is the average frequency across centers and σ^2 is the standard deviation on the logit scale. We calculated that this provides 85% power to detect a 30% relative reduction in the primary outcome (40% down to 28%) if there is significant variation between service lines. If indeed there is no variation between service lines, the power is 98%.

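### Service lines are randomised, but the protocol's primary chi-squared test and the SAP's main between-arm transmission tests have no cluster term, and the SAP does not explain dropping the chi-squared test

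*SAP*

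**What the plan says.** Protocol VI.13 is explicit: "The unit of randomization is the service line".

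Protocol XI.2 (Statistical Analysis) names one primary analysis: "The unadjusted primary intention to treat analysis will compare the proportion of clonally-related S. aureus transmission events" between treatment and control units, "across the 6 randomized service lines using the Chi squared test". A generalised linear model is held back for covariate imbalance: "In the case of imbalance, we will use multivariate techniques to further explore the treatment effect". No cluster term is mentioned for either.

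Protocol XI.2 (Initial Power Analysis) does allow for differences between lines. It takes the line-level logits as normal "with a mean of -0.41 and standard deviation of 0.20", an intra-cluster correlation (ICC) of about 1%. It states 85% power for 40% versus 28% with this variation, and 98% without it. Its number of lines differs from the 6 above: "We intend to screen a total of 1000 patients for up to 10 surgical service lines".

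Protocol XI.1 gives the event definition: a transmission event is "defined as the presence of one or more isolates in a measured reservoir that was not present at case start".

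The SAP (Statistical Analysis) contains no chi-squared test. For treatment versus transmission it gives, in this order:
- "A 2-sided Wilcoxon-Mann-Whitney test was used to examine the association of treatment assignment with the number of transmitted" isolates;
- a Poisson regression with treatment as the independent variable, giving an incidence risk ratio;
- a repeat by multilevel Poisson, clustered by surgeon or specialty.

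Its Fisher tests address other questions: baseline characteristics, covariates, before versus after feedback, and surgical site infection (SSI). Significance is two-sided P < .05.

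**The concern.** When whole service lines are allocated, patients in one line share surgeons, rooms, case mix and baseline transmission. The arms then differ by chance at line level as well as patient level. A test that treats units as independent sees only the second source and understates the standard error. With 6 to 10 lines, a nominally significant result could reflect which lines fell in each arm. The protocol recognises this variation for power but not in the test it names.

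The second problem is the unexplained departure. The SAP's first Poisson model is close to the declared comparison, although the supplied text does not say whether its events are clonally related. The Wilcoxon test is further away: an event needs one or more isolates, so a count of isolates is a different quantity from a proportion with an event. The SAP is in the past tense and reports a finding (no covariate was associated with transmission). Its date alone therefore does not show that these tests were chosen in advance.

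**Working it through.** **Inputs.** 500 patients per arm, 40% versus 28%, SD 0.20 on the logit scale, up to 10 lines (all Protocol XI.2, power analysis); 6 lines (XI.2, Statistical Analysis); two-sided 0.05 (SAP). Assumed: lines split equally between arms (5:5 or 3:3) and, unless stated, equal line sizes.

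**The plan's own figures.** With no line variation, the standard errors for 0.40 − 0.28 = 0.12 are √(2 × 0.34 × 0.66/500) = 0.02996 under the null and √((0.40 × 0.60 + 0.28 × 0.72)/500) = 0.02972 under the alternative. Power = Φ((0.12 − 1.96 × 0.02996)/0.02972) = Φ(2.06) = 98%, as stated.

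For the ICC, σ²p(1−p) = 0.04 × 0.24 = 0.0096, and 0.0096/1.0096 = 0.0095, matching the stated 1% or so.

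The stated 85% was not reproduced. With 10 lines, the unclustered chi-squared test gives 93%, a design-effect calculation 82% and a line-level t-test 73%. With 6 lines these are 90%, 71% and 49%.

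**Chi-squared type I error.** The design effect is DE = 1 + (m − 1) × ICC, with m patients per line. The true error is about 2(1 − Φ(1.96/√DE)).
- 10 lines, m = 100: DE = 1 + 99 × 0.0095 = 1.94; error 16%.
- 6 lines, m = 167: DE = 2.57; error 22%.

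**Unclustered Poisson, model-based variance.** For a yes/no outcome the Poisson variance is too large by a factor 1/(1 − p), which offsets part of the clustering. The net variance ratio is DE × 0.60 = 1.16 (10 lines) or 1.55 (6 lines), so the error is about 7% or 11%.

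**Simulation.** Logit-normal line rates, true null at 40%, 10 lines / 6 lines:

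| Logit SD | Chi-squared | Unclustered Poisson | Line-level t-test |
|---|---|---|---|
| 0.10 | 8% / 10% | 2% / 3% | 5% / 5% |
| 0.20 | 16% / 22% | 7% / 11% | 5% / 5% |
| 0.30 | 26% / 36% | 15% / 23% | 5% / 5% |

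**Sensitivity, all at SD 0.20.**
- Using the protocol's clonal rate (10.58%) and 2,000 units per arm, chi-squared error is about 22% / 30%.
- With illustrative unequal lines (270/150/50/20/10 or 300/150/50 patients per arm), chi-squared error is 25% / 27%.
- Multilevel Poisson on the line, with no small-sample correction, gives about 6% / 9% (1,200 runs only).
- Wilcoxon error was about 15% to 18% / 21% to 25% under several assumed isolate distributions. The documents give no such distribution, so these are illustrative only.

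**Line-level t-test power, 40% versus 28%.** With equal lines (10 / 6): 89% / 73% at SD 0.10, 73% / 49% at SD 0.20, 53% / 32% at SD 0.30. With the unequal lines above, at SD 0.20: about 42% in both cases.

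**The case against.** The strongest reply is that the SAP does address clustering and did not abandon the declared comparison. Much of this stands.

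- A reader might infer that the SAP ignores clustering altogether. It does not: the transmission analysis is repeated with a multilevel model, and specialty is close to the service line. In a past-tense report, surgeon or specialty may mean that both were run. What remains is that surgeon is not the randomised unit, that this is a repeat, and that no small-sample correction is stated.
- A reader might infer that the SAP's results cannot be tied to the declared primary. That is too strong, because the Poisson risk ratio on treatment alone is an unadjusted comparison of much the same kind. The clear change of quantity is confined to the isolate count.
- A reader might infer that no analysis was ever designated primary. The SAP text points to material mentioned earlier that is not supplied, so labels and a clonality definition may sit there.
- A reader might extend the criticism to every unclustered test. The covariate, before/after-feedback and SSI-by-transmission Fisher tests do not compare randomised arms, so the figures here do not apply to them.
- Variation may be smaller than supposed: the protocol expects less after genomic analysis. At SD 0.10 the model-based Poisson is conservative, although chi-squared is still at 8% / 10%. The pilot gives no reassurance in the other direction. Its two main lines showed 28% and 58% on events not yet confirmed as clonal, a logit difference of 1.27, but two lines cannot fix the SD.

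**Conclusion.** The concern holds for the between-arm tests of transmission. The declared chi-squared test and the SAP's Wilcoxon and first Poisson analyses do not reflect randomisation by service line, and the supplied SAP text does not explain why the declared test is absent.

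At the protocol's own SD of 0.20, the declared test's false-positive rate is about 16% (10 lines) or 22% (6 lines) instead of 5%. For the SAP's unclustered Poisson it is about 7% or 11% if the variance is model-based. These figures assume equal lines, a 40% rate and 500 per arm; unequal lines raise the error.

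The size depends on the true between-line SD, which is a supposition, and on the number of lines, which the protocol gives inconsistently. The documents do not show that any reported result is a false positive, and they do not support the view that all the SAP's tests are invalid.

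**What to change.** 1. Keep the Protocol XI.2 endpoint (clonally related transmission, as a proportion) as primary in both documents, and state its analysis unit.
2. Base the primary inference on the service line: either a line-level analysis, such as a t-test on line proportions, or a model clustered on the line with a small-sample correction.
3. Report the declared chi-squared result alongside, and disclose the change as post hoc.
4. Label the isolate-count Wilcoxon, the unclustered Poisson and the surgeon-level model as secondary or sensitivity analyses, and explain each departure from the protocol.
5. Reconcile 6 with up to 10 lines, since both error and power depend on it.
6. Restate power for the line-level analysis, using actual line sizes.

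The cost is wording and a re-analysis of existing data; no new data are needed. Stated power falls from 85% to about 73% or 49% at SD 0.20 with equal lines, and lower if lines are unequal. With a 3:3 split there are 20 possible allocations, so the smallest two-sided exact permutation P is 2/20 = 0.10. Inference would then rest on the assumptions of the t-test or model, and the report should say so.
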